## STATEMENT OF COMPLIANCE

The trial will be carried out in accordance with International Council on Harmonisation Good Clinical Practice (ICH GCP) and the following:

- United States (US) Code of Federal Regulations (CFR) applicable to clinical studies (45 CFR Part 46, 21 CFR Part 50, 21 CFR Part 56, 21 CFR Part 312, and/or 21 CFR Part 812).

National Institutes of Health (NIH)-funded investigators and clinical trial site staff who are responsible for the conduct, management, or oversight of NIH-funded clinical trials have completed Human Subjects Protection and ICH GCP Training.

The protocol, informed consent form(s), recruitment materials, and all participant materials will be submitted to the IRB for review and approval. Approval of both the protocol and the consent form(s) must be obtained before any participant is consented. Any amendment to the protocol will require review and approval by the IRB before the changes are implemented to the study. All changes to the consent form(s) will be IRB approved; a determination will be made regarding whether a new consent needs to be obtained from participants who provided consent, using a previously approved consent form.

## 1 PROTOCOL SUMMARY.

### 1.1 SYNOPSIS

Title:	College Student Stress: Transitions Over Time
Grant Number:	K23 MH131761
Study Description:	
This project will develop a mobile health personalized feedback (PF) intervention for college students at-risk for depressive episodes. Participants will complete daily and weekly assessments, be randomized to receive weekly PF reports regarding mood and stress and be randomized to receive text-messages containing tips/strategies related to self-care, time management, and interpersonal connection/support. We will utilize follow-up surveys and objective indicators of engagement/participation to assess feasibility and acceptability of the intervention. Proposed mechanisms of change (e.g., coping efficacy, perceived stress, readiness for help-seeking) will be assessed by exploring associations of intervention components (i.e., text messages, PF reports) with relevant outcomes.

Objectives:	Demonstrate feasibility, acceptability, and initial impact of mobile health PF intervention on proposed mechanisms of change via a feasibility micro-randomized trial (MRT).
Endpoints:	Participation is complete following the completion of the 6-week follow-up survey.
Study Population:	Participants will be first-year college students, ages 17 or older, recruited from the University of Michigan, Ann Arbor and Flint campuses presenting with mild-to-moderate depressive symptoms who are not receiving professional mental health services.
Phase:	Phase I-II
Description of Sites/Facilities Enrolling Participants:	Participants will be recruited from the University of Michigan, Ann Arbor and Flint campuses via email sent by the university's Registrar.
Description of Study Intervention/Experimental Manipulation:	Participants will be randomized (3:1 intervention-to-control) to receive either 1) weekly surveys only (Assessment-only Condition), or 2) daily and weekly surveys, Personalized feedback reports of symptoms and stress (2:1 randomization to receive/not-receive PF report in a given week), and supportive text messages (2:1 randomization to receive/not-receive messages in a given week; 1:1 daily-level randomization to receive a message during weeks in which randomized to receive messages).
Study Duration:	6 months
Participant Duration:	6 weeks

### 1.2 SCHEMA

### 1.3 SCHEDULE OF ACTIVITIES

	Screening	Baseline Survey	Weekly (Every Sunday for 5 weeks)	Daily (42 days; Intervention-only)	6-week follow-up (6 th Sunday)
Informed Consent	X				
Demographics	X				
Primary Randomization (Survey Only)		X			
Secondary Randomization (MRT)		X			
Outcome Evaluations					
Flourishing Scale	X		X	*	X
Depression (PHQ-9) and Anxiety (GAD-7)	X		X		X
Coping Self-Efficacy	X		*		X
UCLA-Loneliness Scale	X		X		X
Mental Health Service Utilization	X				X
Pittsburgh Sleep Quality Index-Adapted		X	*		X
Physical Activity (YRBS Adaptation)		X	*		X
Interpersonal Needs Questionnaire (INQ)		X			X
DERS-Emotional Awareness		X	X	*	X
Brief COPE		X			X
National Comorbidity Survey (Suicidal Ideation and Behavior)		X	*		*
Perceived Stress Scale		X	*	*	X
Life Events Checklist (LEC-5)		X			
Readiness for Help-Seeking		X	*		X
Daily Mood				*	
Feasibility/Acceptability Survey					X
Adverse Events Reporting		X			X
Note: X = Full-scale; * = Abbreviated version					

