#### 4.4 END-OF-STUDY DEFINITION

A participant is considered to have completed the study when they have completed the 6-week follow-up survey.

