#### 7.3 LOST TO FOLLOW-UP

A participant will be considered lost to follow-up if they do not complete the six-week follow-up assessment.

Before a participant is deemed lost to follow-up, study staff will make up to two telephone contacts and up to two e-mail contacts following the initial survey invitation.

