### 8 STUDY ASSESSMENTS AND PROCEDURES

## 8.1 ENDPOINT AND OTHER NON-SAFETY ASSESSMENTS

To recruit participants, we will obtain e-mail addresses of 2,500 first-year undergraduate students from the registrar (2,000 randomly selected from UM-Ann Arbor, and 500 from UM-Flint, which reflects the full annual enrollment of first-year undergraduate students at the UM-Flint campus) and invite them to participate in an 8-minute survey screen of their mental health, with an online consent form. We anticipate approximately 425 students will consent to participate and complete the **screening survey**, and that 142 students will meet criteria for a positive screen of mild-moderate depressive symptoms (PHQ-9 score of 5-14) and no current psychotherapy for the intervention portion of the study. We anticipate that 85% of the 142 participants who screened eligible for the study will continue to this next phase of the study, provide a cell-phone numbers, and complete the **baseline survey** (all within the same Qualtrics flow of the screening survey). The screening survey will be administered to all invited participants who consent to participate and takes approximately 8 minutes to complete. It will be sent out on a Tuesday, with reminders on Friday, and following Monday. Participants are deemed eligible if they score 5-14 on the PHQ-9, denoting mild-to-moderate depressive symptoms **and** report they are not currently enrolled in a form of mental health care (e.g., therapy). The baseline survey will be administered to participants screening positive on the screen, when they provide their cell phone number, and takes 10-15 additional minutes to complete. Randomization (3:1 to intervention versus assessment-only) occurs after baseline survey has been completed. Daily surveys will be administered to participants in the intervention group only, and take approximately 1 minute to complete, with links to the survey texted at 8pm each day. Weekly surveys are administered to all participants on Sunday evenings and take approximately ten minutes to complete. The final follow-up survey takes approximately 25 minutes to complete and will be administered to all randomized participants (n=120) on their sixth Sunday of the project. Administration of all surveys will be conducted via an online, automated system (Qualtrics).

[figure not shown]

Figure 1. Enrollment Flowchart

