## 8.3 ADVERSE EVENTS AND SERIOUS ADVERSE EVENTS

### 8.3.1 DEFINITION OF ADVERSE EVENTS

An adverse event is any experience or abnormal finding that has taken place during a research project and was harmful to the subject participating in the research, or increased the risks of harm in the research, or had an unfavorable impact on the risk/benefit ratio.

For this study, expected AE include worsening depressive symptoms and onset of suicidal ideation.

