### 8.3.4 TIME PERIOD AND FREQUENCY FOR EVENT ASSESSMENT AND FOLLOW-UP

The occurrence of an adverse event (AE) or serious adverse event (SAE) may come to the attention of study personnel during review of assessments of a study participant or if a participant makes direct contact with study staff through the project e-mail address. All AEs, not otherwise precluded per the protocol, will be captured on the appropriate case report form (CRF). Information to be collected includes event description, time of onset, assessment of severity, relationship to study procedures, and time of resolution/stabilization of the event. All AEs occurring while on study will be documented appropriately regardless of relationship. Within 48 business hours of learning of these events, the coordinator will then bring all possible AEs to the attention of the PI for evaluation and appropriate reporting. AE's will be assessed by the PI for expectedness (expected, unexpected) and relatedness (definitely related, probably related possibly related, unlikely related, not related). A log of all AE's will be maintained by the study coordinator, and the log will be additionally reviewed for completeness at weekly intervals during the active recruitment period.

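### The adverse-event item is scheduled only before randomisation and in the 6-week survey, so no student lost to follow-up can answer it after randomisation

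*Combined protocol and SAP*

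**What the plan says.** **Timing of the item.** The Schedule of Activities (1.3) has one row for "Adverse Events Reporting". It is marked under the Baseline Survey and the 6-week follow-up; the weekly and daily cells are empty. Section 8.1 states: "Randomization (3:1 to intervention versus assessment-only) occurs after baseline survey has been completed".

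**Completion and loss.** Section 4.4: "A participant is considered to have completed the study when they have completed the 6-week follow-up survey". Section 7.3: "A participant will be considered lost to follow-up if they do not complete the six-week follow-up assessment". Before that label is applied, "study staff will make up to two telephone contacts and up to two e-mail contacts following the initial survey invitation".

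**What is to be captured.** Section 8.3.4: "All AEs occurring while on study will be documented appropriately regardless of relationship", with description, onset, severity, relationship and resolution on a case report form. It names two routes by which events reach staff: review of a participant's assessments, and the participant writing to the project e-mail address.

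**Expected events.** Section 8.3.1: "For this study, expected AE include worsening depressive symptoms and onset of suicidal ideation". Sections 1.3 and 8.1 put the full PHQ-9 and two past-week suicidal-thought items in every Sunday survey, for both arms.

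**Review of answers.** Under the safety heading in 2.3.3, participants are told that staff do not watch their survey answers. Section 8.2 says that students who report recent suicidal thoughts are told staff do not look at their responses.

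**Reporting.** Section 8.3.5 promises the IRB a yearly adverse-event summary. Section 9.4.4, Safety Analyses, reads N/A.

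**The concern.** The baseline entry comes before any randomised component, so it cannot record harm from the reports or messages. That leaves one scheduled occasion after randomisation, and it sits in the survey whose absence defines loss to follow-up. Whether a student has an answer to the item is therefore tied, by definition, to whether the student was retained.

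This matters because deterioration can be a cause of loss. Section 7.2 lets an investigator discontinue a student for an event or for newly meeting an exclusion criterion, and a PHQ-9 above 14 is one (5.2). The same worsening can thus be an expected adverse event and the reason no final survey exists. The yearly summary, and the evidence carried into the later trial that 2.3.2 foresees, would then rest mainly on students who stayed.

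**Working it through.** **1. Denominator, reproduced from the plan.** Section 5.5: 2,500 × 17% = 425 screened. 425 × 33% = 140, against 142 stated, which is rounding. 142 × 85% = 120.7, stated as 120. A 3:1 split of 120 gives 90 and 30, as in 4.1 and 9.2. The plan states no retention rate and no adverse-event rate, so everything below that needs them is an assumption.

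**2. Who can answer the item after randomisation.**
- Baseline entry: before randomisation (8.1), so it does not count.
- Weekly and daily columns: empty (1.3).
- 6-week survey: not completed by a lost student (7.3).

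So each lost student has zero post-randomisation answers. With loss fraction d, the number is 120 × d: 6 at 5%, 12 at 10%, 24 at 20%, 36 at 30%.

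**3. What the weekly surveys cover.** The two expected events are asked about each Sunday, so a student lost at week 6 may have up to five sets of answers on them. For those answers to become recorded events, somebody must review them (8.3.4), yet 2.3.3 and 8.2 say they go unwatched or unreviewed, and no section states which change in PHQ-9 or which suicidal-thought answer enters the log. Harms outside these two, such as a hospital admission (serious under 8.3.2) or a bad reaction to a report or message, have no scheduled item before week 6.

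**4. Effect on a count or rate taken from the 6-week item alone.** Let p be the event risk in completers and RR the relative risk in lost students.
- Captured events = 120 × (1 − d) × p
- True events = 120 × [(1 − d) × p + d × p × RR]
- Share missed = d × RR / [(1 − d) + d × RR], which does not depend on p

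With d = 20% and p = 10%, captured = 96 × 0.10 = 9.6.

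| RR | True events | Missed | Captured / 120 | True rate | Completer rate | Error of completer rate |
|---|---|---|---|---|---|---|
| 0.5 | 9.6 + 24 × 0.05 = 10.8 | 1.2 (11%) | 8.0% | 9.0% | 10.0% | +1 point |
| 1 | 9.6 + 24 × 0.10 = 12.0 | 2.4 (20%) | 8.0% | 10.0% | 10.0% | 0 |
| 2 | 9.6 + 24 × 0.20 = 14.4 | 4.8 (33%) | 8.0% | 12.0% | 10.0% | −2 points |

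The count and the rate over 120 are low in every row. The completer rate is high, right or low, depending on RR. Over d from 5% to 30%, p of 10% or 20% and RR from 0.5 to 2, its error runs from +3 points (true rate 20.4/120 = 17%, shown as 20%) to −6 points (true rate 31.2/120 = 26%, shown as 20%), both at d = 30% and p = 20%.

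**5. Comparison between arms.** Take 20% loss in each arm and 15% risk in completers. If lost students in one arm have doubled risk, that arm's true risk is 0.8 × 15% + 0.2 × 30% = 18% against 15%. The true difference is 3 points, in favour of either arm depending on where the doubling lies, while completers show zero.

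**6. With the item added on Sundays.** Each student has up to 6 post-randomisation occasions instead of 1, so up to 720 forms instead of 120. For harms outside the two expected ones, an event on day 1 is now first asked about around day 42, a wait of 41 days. A Sunday item shortens that to at most 7 days when the survey is answered.

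**The case against.** A reader might infer that lost students contribute no solicited harm data. The documents do not support that: the two events the protocol expects are asked about every Sunday. Nor does missing a weekly survey, or being admitted to hospital, take anyone out of the final survey, which goes to all 120 (8.1). Section 7.1 lets students stop texts or reports and stay in the surveys, and reasons for withdrawal are recorded (7.2) and form part of a primary outcome (8.1). These routes could bring some events to light. They do not reach other harms in a student who simply falls silent.

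A reader might also infer that reported harm is biased low in general, or that a third of events would be missed. The first holds only for a count, or a rate over all randomised, from the 6-week item. A completer rate is low only if lost students have more events, which is plausible but has no figure behind it. The one-third result needs both 20% loss and doubled risk, and credits nothing to the other routes. With 9.4.4 at N/A, no harm rate is defined that could be called biased; the yearly IRB summary is nonetheless a planned report of events.

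Two smaller points stand. The row in 1.3 may denote a staff form and not a question to the student, since the measures in 8.1 describe no such question; the timing gap is the same either way. And the statement in 2.3.3 might mean only that nobody watches answers in real time, which would leave room for later review, but neither it nor 8.3.4 says so.

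**Conclusion.** The point holds. Followed as written, the schedule gives every lost student no post-randomisation answer to the adverse-event item: 12 to 36 of 120 at an assumed 10% to 30% loss. The undertaking in 8.3.4 to document all events is then left to unprompted e-mail and to a review of assessments that 2.3.3 and 8.2 appear to rule out.

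That the count, and the rate over 120, from this item are low needs only that some lost student has an event. How low depends on assumed loss and risk: 11% to 33% of events at 20% loss with RR between 0.5 and 2, before any credit for other routes. The direction of error in a completer rate or a between-arm difference cannot be settled from the documents. In a study described as minimal risk, this is a gap in capture and reporting, not evidence that harm is being concealed.

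**What to change.** 1. **Section 1.3:** mark the adverse-event item in the five Sunday surveys that both arms already receive, with recall back to the last survey answered. The baseline entry may stay: 8.3.3.2 judges events against study procedures, and 2.3.1 names distress from the questions as a risk. Describe the item among the measures in 8.1.
2. **Section 7.3:** ask the same item within the telephone and e-mail contacts already provided for, and reconcile those calls with the statement in 8.2 that staff and participants have no direct contact.
3. **Section 9.4.4:** replace N/A with adverse-event counts by arm over all randomised students, the number with no post-randomisation answer, and when each student was last asked. This is needed even with weekly items, because they cannot reach someone who stops answering everything.
4. **Sections 8.3.4, 2.3.3 and 8.2:** reconcile them on whether answers are reviewed, and when. The sponsor should prespecify how weekly PHQ-9 and suicidal-thought responses enter the adverse-event log; no threshold is proposed here.

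The cost is one added item in automated surveys, one question in existing contacts and a short table. Sunday surveys become slightly longer, and the reported count will probably rise because more events are asked about.

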## 2 INTRODUCTION

### 2.1 STUDY RATIONALE

Depression is the #1 cause of disease-related disability worldwide and prevalence rates for depression and suicide have increased significantly in the United States over the past 25 years. Young adults, including college students, have especially high rates of depression, yet most individuals with clinically significant symptoms do not seek formal treatment. College students at elevated risk for suicide may decline formal treatment due to barriers such as lack of time, low perceived need for treatment, or limited access to services. Mobile health technologies offer promising new opportunities to overcome these barriers and improve outcomes. Further, the use of mobile technologies allows for the gathering of real-time subjective data, and an ability to respond to mood changes directly with an intervention at the time it is needed. Yet, engagement with mobile health interventions tends to wane quickly, and it is unclear how these interventions can best be implemented in ways that promote sustained health benefits. The present study seeks to develop a low-burden mobile intervention that can help first-year college students more readily identify negative trajectories in their mental health and take steps to facilitate effective coping and/or seek formal help. This two-arm pilot study, with an embedded micro-randomized trial (MRT), will allow us to 1) evaluate the feasibility and acceptability of the study intervention components, 2) examine the initial impact of the study intervention components on the proposed mechanisms of change, and 3) through a series of micro-randomizations, inform an adaptive intervention design that provides personalized feedback or text messages only when it is expected to have a positive impact.

### 2.2 BACKGROUND

Depression and suicidal ideation among college students have increased significantly over the past decade (Lipson et al., 2019). Evidence-based treatments, including psychotherapy and medication, have demonstrated effectiveness (Allen et al., 2007; Lee et al., 2019), yet college counseling centers have struggled with long waitlists and insufficient staffing, resulting in many students not receiving needed care (e.g., Auerbach et al., 2016; Xiao et al., 2017). In addition to access barriers, many at-risk students report a lack of time and a perception that their symptoms are not serious enough to require treatment (e.g., Epstein et al., 2010). Early intervention can mitigate the risk for future depressive episodes, yet in many cases, individuals are unaware or unable to name their experiences as symptoms of depression until symptoms are severe and causing significant impairment (e.g., Czyz et al., 2013). There is a significant need for effective, accessible interventions that can promote early recognition of symptoms and overcome common barriers to treatment for college students.

With the ubiquity of smartphones in the US across socioeconomic statuses (Pew Research Center, 2021) and mental health patients (Campbell et al., 2015), mobile interventions offer an accessible modality to deliver care. Advances in mobile technologies have significant potential for reducing barriers to treatment for college students. To date, mobile interventions have not taken full advantage of the unique technological opportunities provided by smartphones to enhance engagement. Namely, mobile technology allows for the collection of 'real time' data, which can be used to provide feedback and confront an individual's lack of awareness or perceived need for intervention (Lattie et al., 2019). Utilizing these data can dramatically transform the delivery of mobile interventions through preventive, adaptive approaches, whereby content is optimized and delivered in response to specific emotional or behavioral changes.

Given the stressors associated with beginning college (Byrd & McKinney, 2012), high prevalence and first onsets of depression, and multiple barriers to mental health care, first-year college students are an ideal, at-risk population to target with a low-burden mobile intervention optimized to prevent the negative progression of depressive symptoms. This study will evaluate feasibility, acceptability, and initial effectiveness of the intervention and explore impact on mechanisms of action.

## 2.3 RISK/BENEFIT ASSESSMENT

### 2.3.1 KNOWN POTENTIAL RISKS

The proposed study poses minimal risks. There is a small risk for violation of confidentiality and this risk exists because human participants are providing personal information. Furthermore, as a longitudinal study, we must maintain a link between each student's contact information and their study IDs while the study is active, which is necessary for connecting data at the various follow-up timepoints and providing proper compensation for completed surveys. It also enables us to take appropriate action if a student provides information to suggest imminent risk of suicidal or other dangerous behavior. This risk is related to the damage that could be caused by an inadvertent release of sensitive information (e.g., psychiatric symptoms). Participants will be informed of these risks, the procedures taken to protect their confidentiality, and mandatory reporting requirements in the consent documents. The Risk Management Protocol will be utilized if confidentiality needs to be breached due to a safety concern. Participants could potentially experience emotional discomfort as a result of being asked personal questions about their mental and behavioral health and attitudes related to treatment-seeking. Because the screening portion of the study takes place via Qualtrics surveys, participants will receive crisis and referral information, including local and national resources (e.g., suicide hotlines, crisis text-lines, mental health and substance use treatment, etc.). All participants will also be notified that they are free to terminate the study at any time and may skip any questions that make them uncomfortable.

